9.1.3 Phase 3: Inpatient XR-NTX Dosing (Day 8 or 9)

On day 8, subjects will be offered an injection of XR-NTX following naloxone challenge starting with a split dose an option of 0.2 mg first, wait 10-20 minutes, then 0.6 mg (0.8 mg I.M of naloxone total) An injection of Vivitrol is optional, only if the subject is interested in the XR-NTX treatment), and only if the COWS does not rise above 10 (COWS) within 15-30 minutes after the challenge. Subjects will be offered a second XR-NTX dose in the outpatient research clinic 4 to 5 weeks after the Day 8/9 injection if they wish to continue XR-NTX and have been unable to find a community provider. Subjects who fail the naloxone challenge on Day 8 will receive symptomatic treatment, observed until symptoms resolve, and be offered an opportunity for a repeat

challenge and injection on day 9. Note:

Note: XRNT may be given to patients after a Naloxone challenge in Pts about to go AMA from hospital if the naloxone challenge results suggest an absence of physiologic dependence.

The following assessments will be conducted before the XR-NTX injection:

- 1) CK test drawn before IM Injection of naloxone (PGB can elevate CK)
- 2) Vital Signs (blood pressure sitting)
- 3) Adverse Events Review
- 4) Urine Pregnancy Test
- 5) VAS scale
- 6) ISI
- 7) SOWS-G
- 8) POSS
- 9) UDS
- 10) Urine Fentanyl test
- 11) urine xylazine test
- 12) COWS
- 13) Naloxone Challenge*
- 14) Concomitant Medication Review
- 15) C-SSRS

ADMINISTRATION OF EXTENDED-RELEASE NALTREXONE

The following assessments will be conducted after the XR-NTX injection:

- 1) CGI
- 2) HAM-A, HAM-D
- 3) Inspection of injection site
- 4) Comfort medication(s) (PRN)

(It is permissible to give comfort medication at visit 8 for Day 8, 9, and at Day 10 for visit 10, 11, 12, 13, 14 and 15. No comfort medication will be given by the study after Day 15. Comfort medication needed after Day 15 will be considered non-study follow-up care. Patients can get comfort medications even if they don't opt for XR-NTX).

* Optional. Subject can opt not to receive this treatment. The Study Physician will discuss with the subject other available options. All assessments for Day 8 except the challenge and XR-NTX will still be collected.

9.1.4 Subjects who remain inpatient. Subjects who remain inpatient for a Day 9 naloxone challenge and XR-NTX administration if they are interested but do not qualify on day 8, will be given the challenge as per the procedures for Day 8. Those who fail a second challenge will be counted as having an unsuccessful detoxification and be referred to the most appropriate and available treatment. Subjects will be discharged after the XR-NTX injection (or failed challenge) and asked to return to the study outpatient clinic for their scheduled Day 10, and Day 15 visits according to the intent-to-treat design.

9.1.5 Phase 4: Outpatient Follow-up Visit Assessments (Days 10 and 15)

Assessments at Day 10: (NO POSS)

1) CBC with diff and PLT, chemistry, calcium, UA with reflex microscopy (Magnesium and INR

need not be repeated).

- 2) Fentanyl test (urine)
- 3) Xylazine test (urine)
- 4) UDS
- 5) ISI
- 6) SOWS-Gossop
- 7) COWS
- 8) Vital signs
- 9) Adverse events, concomitant medications
- 10) C-SSRS
- 11) Comfort Medication (PRN)

Assessments at Day 15: (NO POSS)

- 1) Physical/weight
- 2) Urine Pregnancy test for women
- 3) Fentanyl test (urine)
- 4) xylazine test (urine)
- 5) ISI
- 6) SOWS-Gossop
- 7) COWS
- 8) Vital signs
- 9) Adverse events, concomitant medications
- 10) TLFB
- 11) CGI
- 12) HAM-D
- 13) HAM-A
- 14) C-SSRS
- 15) Comfort Medication (PRN)
- 16) UDS

9.1.6 Optional Safety Visit and F/U Day 36 Visit for Second XR-NTX Injection)

Subjects may be asked to come in after the last Day 15 visit for one safety visit, if the PI or study team feels it is necessary, up to 30 days past the end of study visit or 30 days past the F/U Day 36 visit. This safety visit may not be needed for all subjects. The assessments collected will include: CBC, CMP, Ufentanyl, Uxylazine, and a urine drug screen. Compensation will be given for travel.

Subjects may be scheduled to receive a second XR-NTX dose in the outpatient research clinic up to 5 weeks after the Day 8 or 9 injection if they wish to continue XR-NTX and have been unable to find a community provider. Subjects who present for day 36 (+/- 7 days) will undergo the following procedures:

- 1. A urine drug screen
- 2. Pregnancy test (women)
- 3. Naloxone challenge if there is uncertainty about absence of physiologic dependence
- 4. XR-NTX injection

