Pending incarceration in the next 30 days Homicidal or otherwise behaviorally disturbed requiring immediate attention. High Risk for suicide as determined by answering 'yes' to questions 4 and/or 5 on C-SSRS at screening Blood pressure <90 mm Hg (systolic) or <60 mm Hg (diastolic). If this value is out of normal range, the investigator and a study clinician will decide subject inclusion or exclusion on a case-by- case basis Heart rate and/or pulse<50 bpm at screening-sitting An Estimated Glomerular Filtration Rate eGFR<90 mL/min/1.73m² A history of, or current seizure disorder (excluding childhood febrile seizures) Inability to read and/or understand English. For example, does not understand the informed consent as demonstrated by failing to answer 9/10 questions correctly on the guiz Pregnant or breastfeeding Currently taking sympathomimetic drugs, or a thiazolidinedione antidiabetic An ALT and/or AST that is at > 4X the top limit of normal A Child-Pugh score >7 Currently receiving opioids for pain management In a treatment study where medication was administered in the last 30 days. Currently using medications that are known to be strong or moderate inhibitors of CYP2D6 such as fluoxetine, paroxetine, mirabegron, bupropion, quinidine, terbinafine, cimetidine, cinacalcet, duloxetine, or fluvoxamine In a methadone maintenance or buprenorphine treatment program within the last 30 days Pregabalin (PGB) or PGB-PLA given orally at a *starting* dose of up to 400 mg on day 1, up to 600 mg daily on Day 2 through Day 4, tapered to 100 mg daily Study Product, Dose, by Day 7; Lofexidine (LFX) starts at 1.62 mg on day 1, 2.16 Day 2 through Day Route, Regimen 4, tapering to 0.72 mg by Day 7. After starting dose on Day 1, both study drug doses can be reduced or withheld depending upon patient's clinical observations for Days 1-7. On day 8, subjects are offered an injection of XR-NTX if they provide a urine sample that is negative for opioids, buprenorphine, and fentanyl, and pass a naloxone challenge. All subjects, regardless of whether or not they receive XR-NTX, will be given a list of referrals and help with making an appointment for follow-up treatment when they leave the inpatient detoxification program. The following "comfort" medications are suggested for treatment of withdrawal symptoms that are not suppressed by study medications: ondansetron 4 mg or 8 mg tid PO PRN for nausea and vomiting, trazodone 100 mg HS PRN insomnia, loperamide 2 mg qid PO PRN diarrhea, and a non-steroidal such as **Comfort Medications** Ibuprofen 600 mg qid PO PRN for aches and pains or acetaminophen 650 mg (2 tablets 325 mg) PO gid PO PRN, cyclobenzaprine 5 mg tid PO PRN for muscle aches and pains, and hydroxyzine 25 mg qid PO PRN anxiety. In cases of QTc prolongation that are not >550ms or judged to require stopping study medications, diphenhydramine 50 mg hs PO PRN may be used for insomnia, and trimethobenzamide 300 mg gid PO PRN for nausea.

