Adverse Events		1X @each visit	1X @each visit	1X @each visit	1X @each visit	1X @each visit	1X @ea ch visit	1X @each visit	1X @visit	1X @visit	1X @visit	1X @visit
Serious Adverse Events		1X @each visit	1X @each visit	1X @each visit	1X @each visit	1X @each visit	1X @ea ch visit	1X @each visit	1X @visit	1X @visit	1X @visit	1X @visit
Concomitant Medications	1X	1X @each visit	1X @each visit	1X @each visit	1X @each visit	1X@each visit	1X @each visit	1X @each visit	1X @visit	1X @visit	1X @visit	1X @visit
Comfort Medications		1X @each visit	1X @each visit	1X @each visit	1X @each 1 visit	X @each visit	1X @each visit	1X @each visit	1X @visit	1X @visit	1X @visit	
TLFB- 90	1X											
TLFB-2-wk Clinical Global Impression Scale (CGI)	1X								1X		1X 1X	1X
HAM-D	1X								1X		1X	
HAM-A	1X								1X		1X	
C-SSRS	1X	1X	1X	1X	1X	1X	1X	1X	1X	1X	1X	
Lofexidine/Pregabalin* * Adherence Pill Count XR-NTX Adherence		1X	1X	1X	1X	1X	1X	1X	1X			
End of Study Form (EOS)		EOS only completed 1x when subject completes or drops from study at last study visit										

ECG=electrocardiogram (QT/Fri corrected for heart rate with Fridericia formula (QTc = QT/RR(1/3)); *CBC=complete blood count with diff; PLT, INR (INR at screen only); Chemistry for magnesium need not be done at Day 10; DSM-5=Diagnostic and Statistical Manual of Mental Disorders, Fifth Edition; COWS=Clinical Opioid Withdrawal Scale; SOWS=Short Opioid Withdrawal Scale; UDS=urine drug screen; BrAC=breath alcohol concentration; TLFB=Timeline Follow-back; CGI=Clinical Global Impression; C-SSRS=Columbia Suicide Severity Rating Scale; HAM- A=Hamilton Anxiety Rating Scale; HAM- D=Hamilton Depression Rating Scale; POSS=Passero Opiate Sedation Scale; MINI=Mini International Neuropsychiatric Interview

The number prior to X refers to the number of times the procedure is done. Vital signs are done 1X sitting and 1X standing Pre-dose and Post-dose at each daily dose scheduled. **Lofexidine/Pregabalin Adherence is done by pharmacy/site collection of bottles per subject and blister packs for all doses. † Day 9 is used for retests if needed, but all assessments are again done as per day 8 unless otherwise noted.

Illicit non-study concomitant meds are covered in TLFB; UDS, Fentanyl and xylazine test are done at screen, and Day 1, Day 8, Day 10, Day 15; and Early termination.

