10.11 STUDY MEASURES; SEE TABLES 1 FOR SCHEDULES OF ADMINISTRATION

- 1. **Medical History:** Done by the appropriate clinical delegated individual at screening
- 2. Physical/Weight: Done at Screen; and at Day 15
- 3. Pulse and blood pressure: done sitting and standing 1X at screen, done Day 1 through Day 7 done before receiving Study Medication and 1 2 hours after receiving medication, 1X on Day 8, 1X (sitting only) on Day 10 (sitting only), and 1X on Day 15
- 4. ECG: 1X at Screen, 1X each day for Day 1 through Day 7
- 5. Complete Blood Count with diff and PLT: Done at Screening and Day 10
- **6.** Chemistry and calcium: Done at Screening and at Day 10 or Day 15 if not obtained at Day 10
- 7. Magnesium Screening (magnesium need not be repeated at EOS)
- 8. Creatine Kinase at screening and Day 8, and early termination
- 9. Hepatitis B and C done at screening
- 10. Urinalysis with reflex microscopy: Done at Screening and Day 10
- **11. Urine Toxicology Drug Screen.** CLIA Waived and FDA approved on-site test with Buprenorphine, or get an additional buprenorphine test, done at screen, day 8/9, day 10, and day 15.
- **12. Urine Fentanyl**. Done at Screen, Day 1, Day 8/9, Day 10, and Day 15.
- 13. Urine Xylazine . Done at Screen, Day 1, Day 8/9, Day 10, and Day 15.
- 14. Urine pregnancy test: Screen and Day 1, Day 8/9 prior to the XR-NTX injection, and at Day 15
- 15. Adverse Events: Collected by research staff at each visit, Day 1 through Day 15
- **16. Clinical Global Impression Scale (CGI;** Guy,1976): A brief severity rating of overall health at time of interview using a 7-point Likert scale. Completed by a study staff person and the subject. Administered at day 1, day 8, and EOS
- 17. Clinical Opioid Withdrawal Scale (COWS; Wesson & Ling, 2003): An 11-item, staff administered instrument that measures objective signs of opiate withdrawal. Done 1X at screen, 2X daily Day 1 through Day 7, 2X (naloxone challenge) on Day 8* (optional), and 1X on Day 10, and 1X Day 15
- **18. Short Opioid Withdrawal Scale** (SOWS-Gossop; Gossop, 1990): A 10-item, staff administered scale that measures patient's perceptions of opiate withdrawal. Done 1X at screen; 2X daily Days 1 Day 7; and 1X on Days 8,10, and 15.
- **19. CONCOMITANT Medication** (CONMEDS): Any prescribed or non-illicit non-Study Medications used 30 days before screening, and on Day 1 through EOS

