11.9 RULING OUT CURRENT PHYSIOLOGIC DEPENDENCE BEFORE XR-NTX ADMINISTRATION (NALOXONE CHALLENGE)

The COWS will be performed before administering XR-NTX, to assess the subject's signs/symptoms of withdrawal. Naloxone administration should start with a split dose of 0.2 mg first, wait 10-20 minutes, then 0.6 mg (0.8 mg total). Following in the challenge, the patient should be monitored for 15-30 minutes for the appearance of opioid withdrawal. The absence of physiologic opioid dependence is seen by COWS scores that are < /=10. If clinically significant withdrawal is shown, a study physician will treat it with one or more of the approved non-narcotic "comfort" medications.

- 1. Signs and Symptoms of a positive naloxone challenge might include:
 - Objective—tearing, sweating, goose bumps, shakes, vomiting, pupillary dilatation, vital sign increases

11/2/2022

- Subjective—feeling of temperature change, joint and/or muscle pain, bone pain, nausea, abdominal cramping, skin crawling
- 2. If opioid abstinence syndrome is precipitated by naloxone, symptoms will be apparent within a few

Protocol V9.0

minutes and maximal within 20 minutes after administration, but the patient must be observed for 15-30 minutes

If manifestations of opioid withdrawal are evident following the naloxone challenge do not initiate naltrexone therapy due to potential risk of precipitating more severe and prolonged withdrawal with XR-NTX; the naloxone challenge test may be repeated in 24 hours (inpatient Day 9) in these patients.

If withdrawal symptoms are present, the patient should be treated with withdrawal reducing medication or equivalent and observed until symptoms have resolved (about 20 minutes).

If evidence of withdrawal is absent, naltrexone therapy may be initiated. Please note that even minor and/or transient GI symptoms following naloxone challenge be considered evidence of withdrawal since patients with such symptoms will often develop severe and disturbing GI symptoms if XR-NTX therapy is then initiated.

- 3. Signs and Symptoms of positive naloxone Challenge might include:
- Objective—tearing, sweating, goose bumps, shakes, vomiting, pupillary dilatation, vital sign increases
- Subjective—feeling of temperature change, joint and/or muscle pain, bone pain, nausea, abdominal cramping, skin crawling
- 4. If an opioid abstinence syndrome is precipitated by naloxone, symptoms will be apparent within a few minutes and maximal within 20 minutes after administration.

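### The Day 36 checklist orders no urine fentanyl test before the second XR-NTX injection, and its conditional naloxone challenge is looser than section 7.5.2

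*Combined protocol and SAP*

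**What the plan says.** Section 9.1.6 provides for a second XR-NTX injection in the research clinic for patients who have found no community provider. It says: "Subjects who present for day 36 (+/- 7 days) will undergo the following procedures". Four items follow: a urine drug screen, a pregnancy test for women, "Naloxone challenge if there is uncertainty about absence of physiologic dependence", and the injection. Fentanyl is not mentioned. In the same section, the optional safety visit, at which no injection is planned, is to collect "CBC, CMP, Ufentanyl, Uxylazine, and a urine drug screen".

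For the first injection the conditions are fuller. Section 3.0 offers it on Day 8 to patients "if they provide a urine sample that is negative for opioids, buprenorphine, and fentanyl, and pass a naloxone challenge". Figure 1 in 4.0 also names fentanyl among the required negatives, and 9.1.3 lists "Urine Fentanyl test" as a pre-injection item of its own, next to the UDS.

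Section 10.11 describes the UDS (item 11) as a "CLIA Waived and FDA approved on-site test with Buprenorphine, or get an additional buprenorphine test". Urine fentanyl is a separate item (12) with its own schedule. The note to Table 1 says: "UDS, Fentanyl and xylazine test are done at screen, and Day 1, Day 8, Day 10, Day 15; and Early termination". Neither schedule reaches Day 36.

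Three general provisions bear on dependence. Section 7.5.2 has clinicians judge its absence by observation and by a COWS of 10 or less both before and after a naloxone challenge. Section 11.9 says: "The COWS will be performed before administering XR-NTX". Section 7.5.11 rules out XR-NTX in current dependence, in withdrawal, after a failed challenge, or when the urine screen shows opioids.

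**The concern.** By Day 36 the patient has been an outpatient for weeks and may have returned to opioid use. Section 7.5.2 warns that XR-NTX brings on or worsens withdrawal in a dependent patient who has not been opioid-free for 7 to 10 days. If the opioid is fentanyl and the site's UDS does not detect it, the listed urine test would be negative and the bar in 7.5.11 would not be triggered by it. The challenge is ordered only if someone is uncertain, and a fentanyl result is one of the facts that would create that uncertainty. Detection would then rest on history, observation and the COWS.

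What is at stake is the safety of patients who take the second injection. That injection enters no endpoint and no analysis.

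**Working it through.** This is a comparison of texts plus day arithmetic. The plan gives no figure to reproduce.

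**1. Where the protocol orders a UDS, and what goes with it** (Table 1 and its note, 9.1.3, 9.1.5, 9.1.6)

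| Occasion | UDS | Fentanyl test | Naloxone challenge | XR-NTX possible |
|---|---|---|---|---|
| Screen | yes | yes | no | no |
| Day 1 | yes | yes | no | no |
| Day 8/9 | yes | yes | yes | yes |
| Day 10 | yes | yes | no | no |
| Day 15 | yes | yes | no | no |
| Early termination (including leaving AMA) | yes | yes | yes, before any injection | yes |
| Optional safety visit | yes | yes | no | no |
| Day 36 | yes | not listed | only if uncertain | yes |

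Table 1 gives 6 occasions and 9.1.6 adds 2, so 6 + 2 = 8. Seven of the 8 pair the UDS with a fentanyl test. This count describes how consistent the checklists are. It does not measure risk.

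**2. Does the UDS already cover fentanyl?** The protocol lists the two tests separately in Table 1 and its note, in 9.1.3, in 9.1.5, in 10.11 items 11 and 12, and at the safety visit in 9.1.6. Item 11 names buprenorphine as part of the screen and does not name fentanyl. This supports reading them as different tests. On the other side, 8.2 and 9.1.2 define successful detoxification by a drug screen free of opioids, with a trailing phrase on buprenorphine and fentanyl that can be read as making fentanyl one of the screen's results. No section lists the panel. That the UDS misses fentanyl is therefore an assumption.

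**3. Time since the last scheduled fentanyl test**
- Window for the second injection: 36 − 7 = Day 29 to 36 + 7 = Day 43, which is 15 days.
- Gap from nominal Day 15: 29 − 15 = 14 days; 36 − 15 = 21 days; 43 − 15 = 28 days.
- Day 15 itself may run up to 2 business days late.

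**4. Blockade left from the first injection.** Section 7.1 gives at most four weeks (28 days).
- Injected Day 8: 8 + 28 = Day 36. Days 29–36 (8 days) are within that period and Days 37–43 (7 days) are beyond it.
- Injected Day 9: 9 + 28 = Day 37. Days 29–37 (9 days) are within and Days 38–43 (6 days) are beyond.

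**5. Item 3 of 9.1.6 against 7.5.2.** Section 7.5.2 describes the determination as COWS before and after a challenge and sets no Day 8 limit. Section 9.1.6 makes the challenge conditional. The protocol does not say which governs. Either reading is open to a site, and the two differ on whether a challenge is needed.

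**6. Other safeguards.** The COWS in 11.9, observation in 7.5.2, the bars in 7.5.11, and the investigator's freedom in 10.12 to order further tests all apply or can be used. None of them requires a fentanyl test. The COWS scores withdrawal signs at one moment, and 9.1.2 foresees enrolled patients arriving below the withdrawal thresholds, so a low score alone does not show absence of recent use. That example concerns patients not yet given naltrexone, so it carries over to Day 36 only by analogy.

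**The case against.** The strongest case against has five parts.

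- **Section 7.5.2 may already require a challenge.** Its wording is general, and the heading of 11.9 speaks of ruling out dependence before XR-NTX without naming a day, although its repeat instruction refers to Day 9. This stands. A reader of 9.1.6 alone might infer that Day 36 is the one route to XR-NTX that can go ahead with neither a fentanyl test nor a challenge. The documents do not support that outright: it holds only if item 3 of 9.1.6 overrides 7.5.2, which the protocol nowhere states.
- **The UDS may detect fentanyl.** This stands as a possibility, given the wording in 8.2 and 9.1.2. The protocol does not require it, and its schedules treat the tests as separate.
- **Clinicians can order the test anyway.** Section 10.12 allows it. The optional safety visit, which includes fentanyl, may fall up to 30 days after Day 15 (15 + 30 = Day 45), which spans the window. That is permission, not a requirement, and the safety visit is not tied to the injection.
- **The second injection is a different situation.** The first follows about a week after regular use (20 or more of the last 30 days), whereas at Day 36 the patient has already had XR-NTX. On 8 or 9 of the 15 window days the first injection may still be blocking, and precipitated withdrawal needs dependence, not mere exposure. This lowers the likely risk. It does not remove it, because 7.1 gives four weeks as a maximum and item 3 itself foresees possible dependence.
- **It is not a formal visit.** Section 10.9.1 says so. It is still an injection given in the research clinic under a protocol checklist.

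**Conclusion.** The omission is real and rests on the text: the Day 36 list requires no urine fentanyl test before an XR-NTX injection, while 3.0 and Figure 1 require a fentanyl-negative urine before the first. Item 3 of that list is also looser than 7.5.2, and the conflict is unresolved.

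The size is modest. The nominal gap since the last scheduled fentanyl test is 14 to 28 days, 21 at Day 36. The documents give neither the number of second injections nor a fentanyl-positive rate, so no number at risk can be estimated. Confidence is high for the omission and lower for any resulting harm, which depends on two assumptions: that a site's UDS would not detect fentanyl, and that some patients are dependent again by then without showing it on COWS or observation.

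A reader might also infer that the trial's results are affected. They are not: no endpoint, analysis or sample size uses the second injection. This is a safety gap that should be closed because closing it is cheap.

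**What to change.** In 9.1.6:

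1. Reword item 1 as: *A urine drug screen including buprenorphine, and a urine fentanyl test.* Add that a positive fentanyl result counts as a positive opioid screen under 7.5.11, so no injection is given at that visit.
2. Either align item 3 with 7.5.2, so that COWS is recorded before and after a challenge, or state that 9.1.6 governs the second injection and the challenge stays discretionary.

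The first change costs one extra test per second injection, on urine already collected. Sites already run this test at five scheduled visits (Screen, Day 1, Day 8/9, Day 10, Day 15). Some injections would be withheld, including from patients who were exposed but are not dependent. The second change costs nothing if 9.1.6 is declared to govern. If 7.5.2 is followed, it adds a challenge and the 15 to 30 minutes of monitoring described in 11.9. Neither change affects the data, endpoints or sample size.
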